[name]

PERSONAL EMAIL: [contact]

NHS EMAIL: [contact]

[contact]

MR [name]

SPECIALIST REGISTRAR

MERSEY DEANERY, [name],
[name]

PERSONAL EMAIL: [contact]

NHS EMAIL: [contact]

[contact]

MR [name]

CONSULTANT ORTHOPAEDIC SURGEON

BLACKPOOL VICTORIA HOSPITAL, [name]

[name]

PERSONAL EMAIL: [contact]

NHS EMAIL: [contact]

NHS [contact]

NHS [contact]

[contact]

1 Study Summary

Title	Subacromial Injections for Shoulder Subacromial Pain Syndrome – Comparing Anterolateral Versus Posterior Approach
Short Title	Anterolateral Versus Posterior Approach With Steroid Injection For Subacromial Pain Syndrome
Version & Date	Version six, 27 th March 2019
Chief Investigator	Mr [name]
Objectives	To determine if there is any difference in terms of pain relief in patients with shoulder subacromial pain syndrome, when given a steroid injection into the subacromial space via an anterolateral approach compared to a posterior approach.
Hypothesis	That there is no difference in terms of pain relief at 3 months, 6 months and 1 year from an injection via an anterolateral approach compared to one from a posterior approach
Methodology	
Randomised controlled trial.
 
Patients will attend the orthopaedic clinic and if diagnosed with shoulder subacromial pain syndrome, be offered a steroid injection based on clinical needs. If the patient consents to having a steroid injection, he/she will then be invited to participate in the trial – where they will have an injection by one of the two approaches.
 
Initial clinic assessment: The data collected will include the following,
 
• Which arm is afflicted by the syndrome• Left or right handed (i.e. which is the dominant arm)• Has the patient had previous steroid injection – if so, who by and when• Patient to answer an Oxford Shoulder Score (OSS) questionnaire (The questionnaire used for the study will be in the form of a modified OSS (i.e. In addition to the standard OSS we will inquire about general symptoms and signs (pain, stiffness), duration, hand dominance, previous injuries to the shoulder and previous treatments to the shoulder. (See attached questionnaire)• Patient also asked to complete Disabilities of Arm, Shoulder and Hand (DASH) questionnaire and Short Form 36 Health Survey (SF36) 
At the time of injection:
 
• Assessment of pain prior to injection using a visual analogue scale 0-10 (0=no pain, 10=severe pain)• Assessment of how uncomfortable the injection was using a visual analogue scale 0-10 (0=no discomfort, 10=extremely uncomfortable)• Assessment of pain 20-30mins after injection using a visual analogue scale 0-10 (0=no pain, 10=severe pain)• The injection: Given under sterile aseptic non-touch conditions. This is standard practice and is NOT formally part of the study (i.e. patients would be receiving the injection regardless of whether or not they were participating in the study). Please see below for details. 
Follow up clinic assessment (3 months, 6 months and 1 year post injection):

	
 Assessment of pain at 3 months, 6 months and 1 year using a visual analogue scale 0-10 (0=no pain, 10=severe pain) Patient to answer a modified oxford shoulder score (OSS) questionnaire (The follow up questionnaire will be identical to the initial questionnaire but excluding questions on previous treatments, hand dominance, injuries and duration. See attached questionnaire) at 3 months, 6 months and 1 year. Patient to answer Disabilities of Arm, Shoulder and Hand (DASH) Questionnaire and Short Form 36 (SF36) Health Survey (identical to the ones completed before the injection) at 3 months, 6 months and 1 year.
Duration	1 year follow up per patient. 36 months total study duration
Centres	One centre – Orthopaedic department, Blackpool Victoria hospital
Primary End Point	Improvement in the Oxford Shoulder Score (OSS) at 3 months
Secondary End Points	
 Oxford Shouldr Score (OSS) at 6 months and 1 year Pain on visual analogue scale at 3 months, 6 months and 1 year Disabilities of Arm, Shoulder and Hand (DASH) score at 3 months, 6 months and 1 year Short form 36 (SF36) Health Survey at 3 months, 6 months and 1 year.
Participants	
86 in total (43 for each approach)
 
The study statistician has calculated the number of participants needed for the study, so that the study can reliably answer its aims, whilst avoiding wastage of time and resources. Statistical methods have been used for sample size calculation as follows: the standard deviation for change in Oxford Shoulder Score (OSS) at 12 weeks from baseline was obtained from a previous study of steroid injection for shoulder pain (Holt, TA et al[11]). 43 patients in each group are needed based on 80% power for a two sample t-test, detecting a minimal important difference of 6 and a two-tailed significance level of 0.05 with a standard deviation of 9.1. This accounts for 10% attrition between baseline and 3 months as documented in the previous study (Holt, TA et al[11]).

Inclusion Criteria	
 Patient diagnosed with shoulder subacromial pain syndrome Age \geq 18
Exclusion Criteria	
 Age < 18 Lacking capacity/unable to give valid consent for participation Full thickness rotator cuff tear diagnosed on either Ultrasound scan or Magnestic Resonance Imaging Unable to complete follow up Unable to speak or read English
Statistical Analysis	
A statistician has formally calculated the number of patients required for the study. Baseline demographic and clinical variables will be reported using summary statistics. In terms of the primary outcome, the change in total Oxford Shoulder Score from baseline to 3 months post-injection will be compared between the two groups using either the Independent Samples t-Test or Mann-Whitney U Test, with the final choice depending on

an exploration of the data. The same approach will be adopted for secondary outcomes. All analysis will be performed according to the intention to treat principle.

1.1 Flowchart of Treatment Schedule

- STEP 1 - New diagnosis of Shoulder Subacromial Pain Syndrome

Patient presents to orthopaedic outpatient clinic and is diagnosed as having shoulder subacromial pain syndrome, offered and agrees to have a steroid injection

- STEP 2 – Does patient meet inclusion criteria?

NO – does not enter study

[figure not shown]
YES – patient initiated to enter study

[figure not shown]
- STEP 3 – Patient consent and study schedule

Patient agrees and consents – patient participates in study. They will be seen in outpatient clinic approximately 3 months following the injection. Postal questionnaires will be sent out at 6 months and 1 year.

Patient does not agree or consent – patient does not enter study

- Please see flow chart below

2 Overview

Patients who present with subacromial pain syndrome (disorders such as subacromial bursitis, rotator cuff tendinopathy, calcific tendinitis, subacromial inflammation with a partial thickness rotator cuff tear) to the orthopaedic outpatient clinic are treated initially with a subacromial steroid injection in addition to physiotherapy for a period of 3 months. This applies to patients who have had no other treatments previously as well as to patients who have had previous physiotherapy or steroid injections prior to presentation. Patients who do not want to undergo the treatment offered are either treated with simple analgesia, sole physiotherapy or surgery.

When a patient with one of the above conditions agrees to go ahead with a steroid injection followed by physiotherapy, the steroid injection is given at the earliest opportunity. The steroid injection is given into the subacromial space either using the anterolateral (front-side) approach (1 cm below and behind the anterior edge of the acromion with the needle aiming towards the under surface of the acromion) or using the posterior (back-side) approach (1cm inferior and medial to the posterolateral acromial edge with the needle pointing towards the anterolateral aspect of the acromion). The exact approach is determined according to the preference of the person carrying out the injection. As a routine we use a 10ml syringe containing 10mls of 0.25% Marcaine along with 40mg triamcinolone with an 18 gauge (green) needle. It is normal for patients to complain of some discomfort during the injection. If a patient experiences any significant discomfort or they

cannot tolerate the injection for whatever reason, then the injection is discontinued and is not reattempted using a different approach.

Following the injection, patients are questioned on any discomfort experienced during the injection and on whether or not their pain has improved. They are then taken through a protocol of physiotherapy for their shoulder over the subsequent 3 months. A protocol is issued for guidance however therapists are allowed to use other modalities as per their discretion. The frequency of appointments with physiotherapy will depend on patient's symptoms as well as their progression. For study purposes a frequency record of these meetings will be kept and matched to the overall OSS. Patients are seen routinely in 3 months following an injection in order to assess any improvement in symptomatology using the OSS, visual analogue score, DASH and SF36 questionnaires. If the symptoms have improved then no further intervention is taken. Further OSS, visual analogue pain score, DASH and SF36 questionnaires will be posted out at 6 months and 1 year. On the other hand, if they are still troubled with symptoms then the possibility of further injections or surgery is discussed.

The aim of this study is to compare the two approaches that are currently used for subacromial steroid injections, namely the anterolateral and posterior approach, with regards to their effectiveness in improving shoulder symptoms. There will be no deviation from our routine protocol other than randomising patients who agree to participate in this study to either the anterolateral or posterior approach.

In summary, it is patients who are seen in clinic with a subacromial pathology and subsequently diagnosed with shoulder subacromial pain syndrome, who are offered an injection. Those who agree to have an injection will then be invited to participate in the study. An information leaflet will be given to all potential participants and they will be allowed sufficient time to read through it, digest all the information and ask any questions they may have before making a decision regarding their participation. Those who agree to participate will be randomly allocated, using sealed envelopes to one of the two approaches for the injection. The injection will then be administered via the selected approach by a clinician who is qualified in carrying out the procedure. Patients will be asked about any discomfort experienced during the injection, improvement in pain following the injection prior to leaving hospital and overall satisfaction with the injection. Following this patients will have physiotherapy as an outpatient as routine and will be seen at about 3 months post injection for a further assessment at the clinic. Again the shoulder assessment will be repeated on that occasion. Shoulder assessment questionnaires will be posted out for completion at 6 months and 1 year (OSS, pain on visual analogue scale, DASH and SF36) There will be no change in patients care from routine practice other than the randomisation of the approach used for the injection. Patients who are invited to participate in the study and agree to participate will have their GP informed of their participation.

Assessments

1. Prior to injection: assessment of pain using a visual analogue score, clinical assessment of shoulder movement and completion of a modified Oxford Shoulder Score, Disabilities of Shoulder, Arm and Hand questionnaires and Short Form 36 Health Survey.
2. 20-30 minutes Post injection: assessment of pain using a visual analogue score
3. Prior to leaving hospital: pain experienced during the administration of the injection and the overall satisfaction with the injection

4. 3 months post injection: assessment of pain using a visual analogue score, clinical assessment of shoulder movement and completion of a modified Oxford Shoulder Score, Disabilities of Shoulder, Arm and Hand questionnaires and Short Form 36 Health Survey.
5. 6 months and 1 year post injection: assessment of pain using visual analogue score and completion of a modified Oxford Shoulder Score, Disabilities of Shoulder, Arm and Hand questionnaires and Short Form 36 Health Survey via post.

The main outcome for this study will be the Oxford Shoulder Score (OSS) at 3 months post-injection. In addition to the standard OSS, the questionnaire will inquire about general symptoms and signs, duration, hand dominance, previous injuries to the shoulder and previous treatments to the shoulder. The follow up questionnaire will be identical to the initial questionnaire but excluding questions on previous treatments, hand dominance, injuries and duration. (See attached questionnaires).

Other demographics that will be recorded on the pre-designed pro forma include: number and frequency of physiotherapy sessions pre and post injection, and subsequent need for further management (see attached).

Hard copies of data (questionnaires and forms) collected will be placed into the patient's notes. At the same time this data will be recorded electronically on an Excel database and saved on an encrypted, password protected memory stick. This memory stick will be stored in a locked filing cabinet in the orthopaedic department at Blackpool Victoria Hospital. Please note: The electronic data will contain NO identifiable information. Participants will be identified by a unique study I.D number which can only be linked to them by members of the research team.

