3.3 Secondary Study Endpoints

Secondary end points include Oxford Shouldr Score (OSS) at 6 months and 1 year, pain on visual analogue scale at 3 months, 6 months and 1 year, Disabilities of Arm, Shoulder and Hand (DASH) questionnaire at 3 months, 6 months and 1 year and Short Form 36 (SF36) Health Survey at 3 months, 6 months and 1 year.

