3.8 Informed Consent

Informed consent will be obtained during the initial clinic visit after the patient has had adequate time to read the information leaflet, digest the information provided and ask any questions they may have, as well as express their views/wishes. The patient will be asked to sign a consent form indicating they have understood all aspects of the study and their rights. This form will also be signed by the researcher and three copies of this form will be obtained (one for patient, one for researchers which will be stored in the study site file and one for the clinical notes).

Withdrawal of Subjects

Patient will be free to withdraw from the study at any time without explanation and without prejudice. A patient will be withdrawn from the study, if unable to tolerate the injection or does not comply with physiotherapy. Abrupt termination of patient from study will not put the patient at risk. The patient will still be offered care as they would be routinely, if unable to continue in study for whatever reason.

If patient fails to attend the follow up clinic visit then a letter will be sent to the patient and copied to the GP as is done routinely when a patient does not attend. A follow up appointment will then be booked for the nearest possible date.

4 Prior and Concomitant Therapy

There are no restrictions to prior or concomitant medicines permitted during the study.

The only therapy that patients will receive will be physiotherapy.

5 Laboratory Assays

Not applicable

6 Study Procedures

All relevant procedures are detailed above.

7 Statistical Plan

The study statistician has calculated the number of participants needed for the study, so that the study can reliably answer its aims, whilst avoiding wastage of time and resources. Statistical methods have been used for sample size calculation as follows: the standard deviation for change in Oxford Shoulder Score (OSS) at 12 weeks from baseline was obtained from a previous study of steroid injection for shoulder pain (Holt, TA et al[11]). 43 patients in each group are needed based on 80% power for a two sample t-test, detecting a minimal important difference of 6 and a two-tailed significance level of 0.05 with a standard deviation of 9.1. This accounts for 10% attrition between baseline and 3 months as documented in the previous study (Holt, TA et al[11]).

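### The 6-month and 1-year hypothesis credits later scores to the first injection, although patients still troubled at 3 months may by then have had further injection or surgery

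*Combined protocol and SAP*

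**What the plan says.** The Hypothesis row of section 1 states "no difference in terms of pain relief at 3 months, 6 months and 1 year from an injection via an anterolateral approach" compared with a posterior one. Section 3.3 makes the late scores endpoints: "Secondary end points include Oxford Shouldr Score (OSS) at 6 months and 1 year", together with pain, DASH and SF36 at the same times.

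Section 2 (Overview) describes what follows the 3-month visit. For improved patients: "If the symptoms have improved then no further intervention is taken". For the others: "if they are still troubled with symptoms then the possibility of further injections or surgery is discussed". The clinician part of the follow-up clinic questionnaire lists a further injection and listing for surgery among the possible decisions, beside no further treatment and continued physiotherapy.

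Section 4 says: "The only therapy that patients will receive will be physiotherapy".

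The decision at 3 months is recorded. Section 2 lists "subsequent need for further management" with the other demographics on the pro forma. It is not an endpoint in section 1 or section 3.3, and section 7 gives it no analysis. Section 7 compares secondary outcomes as it does the primary, by t-test or Mann-Whitney U test under intention to treat. It does not say what a score obtained after a further injection or an operation is taken to mean.

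**The concern.** Further treatment is not spread evenly over the patients. It is raised with those who did badly and not with those who did well. If one approach fails more often, more of its patients become candidates for it, and if it works their later scores rise. The two arms then move towards each other for a reason that has nothing to do with the lasting effect of the first injection.

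The hypothesis is one of no difference, so this movement runs towards confirming it. A null result at 6 months or 1 year could be reported as showing that the approach does not matter, when one approach had led to more repeat injections or operations. The plan collects a 3-month decision that would help the reader tell these apart, but does not compare it between the arms.

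**Working it through.** **The plan's own figure.** Section 7 gives a difference of 6, SD 9.1, two-sided 0.05, 80% power and 10% attrition to 3 months. The two-sample t-test needs 37.09, so 38 per group; 38/0.90 = 42.2, so 43. The stated 43 per group reproduces. It concerns the 3-month endpoint and is not in question.

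**The passages side by side.**

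| Place | Content |
|---|---|
| Section 1, Hypothesis | Relief at 6 months and 1 year attributed to an injection by one approach |
| Section 2, after 3 months | Nothing more if improved; further injection or surgery discussed if not |
| Follow-up form, clinician part | Further injection and listing for surgery are among the decisions |
| Section 4 | Physiotherapy is the only therapy |
| Sections 1 and 3.3 | Further treatment is not an endpoint |
| Section 7 | Same two-group test, intention to treat; no word on scores after further treatment |

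The second and third rows cannot both stand with the fourth, because participation lasts 1 year (section 3.4).

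**How far a difference could shrink.** The documents give neither uptake nor benefit of further treatment, so this is an illustration. It uses the OSS because that is the scale for which the plan states an SD and a minimal important difference.

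From the plan: SD of change 9.1; difference 6.

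Assumed: mean improvements of 10 and 4 points; patients improving by less than 6 points count as still troubled; a share u of them is treated further; each treated patient gains g points; changes otherwise persist.

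1. Share still troubled, better arm: Φ((6 − 10)/9.1) = Φ(−0.440) = 0.330.
2. Share still troubled, worse arm: Φ((6 − 4)/9.1) = Φ(0.220) = 0.587.
3. Gap between arms: 0.587 − 0.330 = 0.257.
4. Late difference = 6 − g × u × 0.257.

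| Gain g | Uptake u = 0.5 | Uptake u = 1 |
|---|---|---|
| 5 | 5.4 | 4.7 |
| 8 | 5.0 | 3.9 |
| 10 | 4.7 | 3.4 |

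The late difference lies between 3.4 and 5.4 points. With assumed means of 12 and 6 and the same cut-off, the shares are 0.255 and 0.500, the gap is 0.245, and the range is 6 − 10 × 0.245 = 3.5 to 6 − 2.5 × 0.245 = 5.4. The result hardly depends on which pair of means is taken.

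**Boundary case.** If both arms use further treatment equally and gain equally from it, the gap is zero and the difference stays at 6.

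**The case against.** The strongest reply is that the trial already compares strategies. Section 2 says that care departs from routine only in the randomised approach, and section 7 analyses by intention to treat. Together these imply first approach followed by usual care, which is a legitimate question. That stands: the analysis is valid and should be kept. But the protocol does not say that this is its late question, and the hypothesis wording points to the injection itself.

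The second reply is that the primary endpoint protects the main conclusion. It is measured at 3 months, at the visit where further treatment is decided, and would be reported beside the late scores. That also stands, and it confines the point to secondary endpoints.

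Third, section 4 might be meant for the first 3 months only. It does not say so.

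Three stronger readings are tempting, and the documents do not support them.

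- **That masking will occur.** Section 2 says only that further treatment is discussed, and the form also allows none. Masking needs a true difference between approaches, unequal further treatment and benefit from it. None of these is established.
- **That repeat injections cross over to the other approach.** The sentence "The exact approach is determined according to the preference of the person carrying out the injection" describes routine injections. No text says which approach a repeat injection uses, so crossover is possible but only inferred.
- **That late power drops by a definite amount.** Putting the smaller difference into a t-test with SD 9.1 ignores that raising only the poor responders also narrows the spread. In the scenario above with g = 8, full uptake and changes carried forward, the SD falls to about 6.5. Power then depends on the late SD and on the correlation between 3-month and later change, and the plan gives neither. No power figure should be quoted.

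**Conclusion.** The point holds as a matter of what the 6-month and 1-year results can be said to show. The late hypothesis credits the scores to the first injection, later treatment depends on the 3-month outcome, and the plan neither states how such scores are to be read nor compares the recorded decision between arms. Under the assumptions shown, a true difference of 6 OSS points could be attenuated to about 3.4 to 5.4; it is reduced, not erased, and not reduced at all if further treatment is equal in use and benefit. The 3-month primary endpoint and the sample size are unaffected. Separately, and without any assumption, section 4 contradicts section 2 and the clinician form. This is a change that should be made to secondary endpoints; it is not a flaw in the main comparison.

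**What to change.** 1. Add to the secondary endpoints in sections 1 and 3.3 the proportion per arm with a decision for further injection or listing for surgery, taken from the existing 3-month clinician form, with a risk difference and 95% CI. State that it records a decision at 3 months, not treatment received later, and that patients who do not attend have no entry. It therefore cannot show whether treatment came before a given 6-month or 1-year score.
2. Keep the intention-to-treat analysis, but word the 6-month and 1-year hypothesis as first injection anterolateral versus first injection posterior, each followed by usual care. Report the late scores beside the proportions in item 1.
3. Reconcile section 4 with section 2 and the clinician form. Which of them describes the intended care is for the investigators to state.

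The cost is protocol wording and one table from data already collected, with no new visits, patients or forms. The downside is one more secondary outcome and a narrower long-term claim.
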